For women not already receiving extended duration therapeutic anticoagulant therapy who have a history of VTE that was unprovoked or associated with a hormonal risk factor, the ASH guidelines recommend postpartum anticoagulant prophylaxis for 6 weeks. VTE occurring within 6 weeks postpartum affects 6.5% of pregnancies in women with a history of VTE (95% CI, 4.3%-9.7%) (Rodger *et al.*, 2014), compared with a risk of approximately 0.6 of every 1000 deliveries for the general population (Tepper *et al.*, 2014; Kourlaba *et al.*, 2016; Parunov *et al.*, 2015; Kamel *et al.*, 2014). Overall, the incidence during the 1st week postpartum is 9 in 10,000 deliveries, reducing to 2.5 and 1.5 in 10,000 by the 2nd and 3rd week postpartum, respectively (Tepper *et al.*, 2014). In women with a history of VTE who were treated with postpartum prophylaxis (LMWH, UFH), the risk of postpartum VTE was substantially lower at 1.7% (95% CI, 1.2%-2.7%) (Roger *et al.*, 2014), representing a decrement in risk similar to that seen with extended LMWH prophylaxis after high-risk orthopedic procedures (Hull *et al.*, 2001). In the presence of a high-risk thrombophilia and LMWH prophylaxis postpartum, the pooled VTE incidence was 0.2% (95% CI, 0%-1.2%).

In contrast to LMWH, which is expensive and requires daily subcutaneous injections, ASA is an inexpensive, generic, and widely available oral antiplatelet drug. Furthermore, in the postpartum period LMWH is associated with a 0.3% (95% CI: 0%-1%) risk of major bleeding events, 1.8% risk of skin reactions and wound complications after cesarean delivery. ASA use compared to placebo in the antenatal period did not demonstrate increased bleeding complications in 798 patients, with no gastrointestinal (GI) bleeding noted (Rolnik *et al.*, 2017), and in the orthopedic setting with a two-week administration post total knee

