Patients will be identified in the Hematology Clinic of the Special Program at Mount Sinai Hospital, where consent will be obtained. Patients will be randomized immediately following consent. Randomization has been developed for RedCap to allocate the patient into one of the two strategies in a 1:1 ratio, with the assistance of a statistician from Princess Margaret Hospital. Following delivery, the research assistant will dispense the assigned medication to the participant. Blinding or masking of treatment allocation will not be used in the pilot but a placebo control for ASA is intended for the definitive trial.

Baseline Assessment

Baseline assessments will be undertaken at the time of randomization and include age, weight, parity, indication for VTE prophylaxis, gestational age at delivery, medications and delivery complications. Baseline laboratory tests at the time of delivery will include complete blood count, serum creatinine level, coagulation profile and alanine aminotransferase. This limited testing is intended to reflect a pragmatic approach to this trial.

Primary Outcomes:

1. Potential enrollment rate (patients eligible)
2. Consent rates (patients approached/consent obtained/rationale for non-consent)
3. Adherence to study protocol (incidence and reasons for nonadherence, withdrawal of consent, rates of contamination and utilization of co-interventions).
4. Missing data

Secondary Outcomes:

1. VTE event rate three months following delivery
2. Bleeding event rate three months following delivery
3. Quality of life (QoL) assessment using the modified Duke Anticoagulation Satisfaction Scale (Appendix) at delivery and three and six weeks postpartum

Confirmation of VTE

VTE must be confirmed either by Doppler ultrasound or V/Q scan or computer tomography (CT). Imaging will not be performed on all patients, only those with symptoms. For the definitive trial, imaging will be adjudicated.

Bleeding outcomes

Bleeding will be reported according to the International Society on Thrombosis and Hemostasis (ISTH) scoring system (<https://bleedingscore.certe.nl/>) (Schulman *et al.*, 2005; Schulman *et al.*, 2009). Bleeding will be assessed at 3 and 6 weeks postpartum using a telephone questionnaire.

Follow up duration

All patients will be followed until 3 months postpartum. Patients will be contacted by telephone at 3 weeks, 6 weeks and 12 weeks after delivery.

Participant trial discontinuation

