Participants may discontinue the study at any time. The participant will immediately discontinue the study medication, and the patient will be treated according to the standard of care. The patient will have a discontinuation telephone follow-up visit.

Statistical analysis

The analysis of this trial is mainly descriptive, as this is a pilot study to ensure adequate enrollment and adherence. All demographics and baseline characteristics will be summarized using mean, median, standard deviation, minimum and maximum for continuous variables, and frequency and percentages for categorical variables. The feasibility outcomes (primary outcomes) will be summarized using frequency counts and percentages with associated 95% confidence intervals.

The definitive trial is designed to show the non-inferiority of a combination of LMWH and ASA over LMWH in decreasing the incidence of composite VTE. However, for the pilot study, the clinical endpoints will only be presented using descriptive statistics. In the definitive trial, VTE, bleeding, and

event-free outcomes will be compared between the two arms using a stratified log-rank test. A non-inferiority margin of 1.0 % will be used based on expert opinion. Statistical analysis will be carried out using SPSS statistical software.

The feasibility trial will be deemed a success and will proceed to a full trial under the current protocol if all the criteria below are met:

- Participant recruitment is > 60%
- Participant adherence to study drug > 80%
- Compliance with study procedures > 80%
- Proportion of participants lost to follow up <25%

Sample size calculation: I plan to recruit 50 patients, 25 patients treated according to each strategy. The outcomes from these patients will be included in the definitive trial.

Recruitment rate: Recruitment is anticipated to be completed in 18 months as we anticipate to enroll 1 patient/week.

Trial registration: The trial will be registered at www.clinicaltrials.gov.

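### The rule for proceeding to the full trial contains no accrual rate or time limit, so it cannot detect enrolment that is too slow, and the accrual plan beside it is internally inconsistent

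*Protocol*

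**What the plan says.** The Statistical analysis section of the protocol states that the pilot is a success and "will proceed to a full trial under the current protocol if all the criteria below are met". Four criteria follow:

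- "Participant recruitment is > 60" (per cent)
- "Participant adherence to study drug > 80" (per cent)
- "Compliance with study procedures > 80" (per cent)
- loss to follow-up below 25%

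Under Primary Outcomes, the first item is "Potential enrollment rate (patients eligible"), listed separately from consent rates, which are the second item. The Aim names enrolment as a question that the pilot addresses for the definitive trial, and the Statistical analysis section gives adequate enrolment as a reason for the pilot.

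After the rule, the Recruitment rate paragraph says: "Recruitment is anticipated to be completed in 18 months as we anticipate to enroll 1 patient/week". This is an expectation, and nothing follows if it is missed.

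For the definitive trial the protocol gives a margin ("A non-inferiority margin of 1.0 % will be used based on expert opinion"). The Background gives event rates under prophylaxis: for women with a history of VTE, "the risk of postpartum VTE was substantially lower at 1.7% (95% CI, 1.2%-2.7" (per cent), and for high-risk thrombophilia 0.2% (0% to 1.2%). It states no definitive sample size, alpha or power.

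**The concern.** All four criteria are proportions of people already found. None says how fast they were found. A pilot that took several years to enrol its 50 women could meet every criterion, be declared a success and move to the full trial with no change of plan.

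This is more than detail left for later. The protocol writes the rule out in full and makes it sufficient for progression. For a non-inferiority trial with rare events, the number of women randomised per centre per month largely fixes how many centres and years are needed. The pilot is meant to measure that quantity, but the decision rule does not use it.

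**Working it through.** **1. Does any criterion respond to time?** Take the recruitment criterion as consented divided by approached. With 50 enrolled:

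- 50/80 = 62.5%: passes
- 50/83 = 60.2%: passes
- 50/84 = 59.5%: fails

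Elapsed time does not enter. At 50 per year or at 12.5 per year (50 over four years) the result is the same. The adherence, compliance and follow-up criteria are also proportions of enrolled women, so slow accrual does not in itself fail any of them.

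**2. The plan's own accrual figure.** Inputs: 50 women, 1 per week, 18 months (Sample size calculation and Recruitment rate). With 52.18 weeks per year, 18 months is 78.27 weeks.

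- 50 / 1 per week = 50 weeks, or 11.5 months, so the stated 18 months is not reproduced.
- 1 per week for 18 months gives 78 women, not 50.
- 50 / 78.27 = 0.64 per week; 50 / 18 = 2.8 per month; 50 / 1.5 = 33.3 per year.

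The figures would agree if 1 per week meant women approached and about 64% consented (50/78), but the sentence speaks of enrolling.

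**3. Why the rate matters for the definitive trial (illustration).** From the protocol: margin 1.0%, event rates 1.7% and 0.2%, 1:1 allocation. Assumed: the margin is an absolute difference, one-sided alpha 2.5%, power 80%, equal true rates, and a comparison of proportions as an approximation to the planned time-to-event analysis.

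n per arm = (1.960 + 0.842)² × 2 × p(1 − p) / 0.01²

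At p = 0.017: 7.849 × 2 × 0.017 × 0.983 / 0.0001 ≈ 2,623, which rounds up to 2,624 per arm and 5,248 in total.

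Centre-years are the total divided by 52.18 per year (1 per week) or 33.3 per year (50 per 18 months):

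| Event rate | Total N | Centre-years at 1 per week | Centre-years at 50 per 18 months |
|---|---|---|---|
| 1.7% (prior VTE) | 5,248 | 101 | 157 |
| 1.0% (mixed population) | about 3,110 | 60 | 93 |
| 0.2% (thrombophilia) | 628 | 12 | 19 |

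The 1.0% row corresponds to (1.0 − 0.2)/(1.7 − 0.2) = 53% of women with prior VTE, if the two Background rates apply.

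**4. Sensitivity to the assumed alpha and power, at 1.7%.**

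- One-sided 2.5%, 90% power: N = 7,024 (135 and 211 centre-years).
- One-sided 5%, 80% power: N = 4,134 (79 and 124 centre-years).
- Counting the 50 pilot women towards N, as the protocol intends, saves 1 to 1.5 centre-years.

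**5. A slow pilot.** At 0.25 per week the pilot takes 50/0.25 = 200 weeks, or 3.8 years. A definitive N of 5,248 would then need 5,248 / (0.25 × 52.18) = 402 centre-years. No listed criterion would fail because of this.

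**The case against.** The strongest case on the other side has four parts.

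*Enrolment would be visible anyway.* It is a primary outcome, a duration is stated, and the Significance section says that the results will inform the definitive design. The first primary outcome, with its bracketed reference to eligible patients, may also be a count rather than a rate over time. This is fair, and nobody would be blind to slow accrual. But the protocol makes the four criteria sufficient to proceed, and visibility is not a threshold.

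*The 60% may already contain a rate.* If it meant more than 60% of the planned 50 within 18 months, it would require more than 30 women in that time, or 20 per year. At N = 5,248 that floor is 262 centre-years. The text does not say this, and the consent outcome makes a consent proportion the more natural reading. That two readings are possible is itself a reason to define the denominator.

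*The definitive trial's size is not the protocol's own figure.* This stands. Alpha and power are assumed, and 1.7% applies only to women with prior VTE, while the inclusion criteria also admit thrombophilia, for which the Background gives 0.2%. A reader might infer that the protocol's figures imply 100 centre-years or more. They do not: a mixed population at 1.0% gives 60 at 1 per week, and one-sided 5% with 80% power gives 79 even at 1.7%.

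*Nothing shows that the definitive trial cannot be completed.* This also stands. A reader might infer impossibility, but the Significance section plans a multicentre trial. About 100 centre-years is 20 centres for five years, and one centre's accrual does not fix that of the others.

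**Conclusion.** The point holds as a defect of the decision rule. The protocol states in full a rule sufficient for progression, and that rule has no accrual rate and no time limit, although adequate enrolment is one of the pilot's stated purposes. On the natural reading of the 60% criterion, the same 50 of 80 passes after one year or after four. Separately, the accrual plan is inconsistent by arithmetic alone: 50 weeks against 18 months, or 1 against 0.64 per week.

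The size of the consequence is only illustrative. It runs from about 630 to about 5,250 women across event rates of 0.2% to 1.7%, under an absolute margin, one-sided 2.5%, 80% power and equal true rates. These figures show why a per-centre rate belongs in the rule. They do not show that the full trial is infeasible. Participant safety is not affected.

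**What to change.** Make three changes in the Statistical analysis and Recruitment rate text:

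1. State the denominator of the 60% criterion (eligible, approached or planned women).
2. Reconcile 1 patient per week with 18 months, and say whether the weekly figure counts women approached or women randomised.
3. Add a criterion for the number randomised at this centre within a fixed window, taken from the reconciled plan. If 18 months is kept, this is 50 women within 18 months, at least 2.8 per month. If it is missed, the trial does not proceed under the current protocol without review.

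Report the observed rate with the implied number of centres and years for the definitive trial, stating the event rate, alpha and power used. This is needed because the threshold alone does not settle feasibility: 50 in 18 months is the rate at which the 1.7% case takes 157 centre-years.

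The cost is a few lines of text and no added burden on participants. Eligible and approached counts are already primary outcomes, and randomisation through RedCap should supply the dates. The downside is that the pilot can now fail on accrual. A centre whose true rate equals the plan is roughly as likely to miss the threshold as to meet it, which is why a miss should prompt review rather than an automatic stop.

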Participant	Screening Week -8 to Day -1	Dosing Day 1	3-week phone call ± 5 days	6-week phone call (end of study) ± 5 days	3-month phone call ± 5 days	Early discontinuation visit
Informed Consent	X	---	---	---	---	---
Inclusion / Exclusion criteria and Eligibility	X	---	---	---	---	---
Baseline demographics	X	---	---	---	---	---
Concurrent medications	X	---	X	X	X	X
Weight/BMI	X	X	X	X	X	X
Delivery Data: Type of Delivery/ Complications	---	X	---	---	---	---
Laboratory Data: Complete blood count / Creatinine / INR / aPTT / ALT	---	X	---	---	---	---
Drug dispensation	---	X	---	---	---	---
Adherence assessment	---	---	X	X	---	X
Bleeding Assessment Score	---	---	X	X	---	X
Quality of life assessment	---	---	X	X	---	X

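### No go criterion is tied to missing data, a primary outcome, and the schedule has no VTE or bleeding item at 3 months, so the pilot could proceed without showing that these outcomes can be collected

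*Protocol*

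**What the plan says.** Protocol, Primary Outcomes, lists four feasibility outcomes, the last being "4. Missing data". No definition or threshold goes with it.

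Protocol, Statistical analysis, states that the trial "will proceed to a full trial under the current protocol if all the criteria below are met". The criteria are:

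- "Participant recruitment is > 60" per cent
- "Participant adherence to study drug > 80" per cent
- "Compliance with study procedures > 80" per cent
- "Proportion of participants lost to follow up <25" per cent

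The same section has the primary outcomes reported as counts and percentages with 95% confidence intervals. It does not define compliance with study procedures.

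Protocol, Secondary Outcomes, sets the VTE and bleeding event rates at three months after delivery. Protocol, Bleeding outcomes, places the bleeding questionnaire at 3 and 6 weeks. In the Trial Schematic Timeline, the "Bleeding Assessment Score" row is marked at the 3-week call, the 6-week call and early discontinuation, but not at the 3-month call. No row covers VTE. The 3-month call carries only concurrent medications and weight/BMI.

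Under the sample size heading, the outcomes of the 50 pilot women are to be included in the definitive trial.

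**The concern.** A go rule should turn on the feasibility outcomes that the pilot declares as primary. Here one of the four has no criterion of its own, and the two criteria closest to it measure something else. Loss to follow-up counts women, so a woman who is reached by telephone is not lost, whatever was or was not asked. Compliance with procedures is a single figure, and nothing says that an outcome form weighs more in it than a weight or a medication list.

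At stake is whether a pass says anything about ascertainment of the outcomes on which the definitive trial depends. That trial compares VTE between the arms with a non-inferiority margin of 1.0%, and it takes in the pilot women's outcomes. For scale, one woman of 50 with unknown VTE status is 2% of the pilot.

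**Working it through.** The four thresholds and the sample size of 50 are set without a calculation, so there is no stated figure to reproduce. The check asks what the go rule can detect.

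**Step 1. Match primary outcomes to criteria.** Recruitment relates to enrollment and consent (outcomes 1 and 2). Drug adherence and compliance with procedures relate to adherence to the protocol (outcome 3). Loss to follow-up touches withdrawal and, indirectly, missing data. No criterion is stated for outcome 4.

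**Step 2. Count the scheduled items** in the Trial Schematic Timeline for a woman who does not discontinue early.

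| Contact | Items | Of which bleeding | Of which VTE |
|---|---|---|---|
| Screening | 5 | 0 | 0 |
| Dosing day | 4 | 0 | 0 |
| 3-week call | 5 | 1 | 0 |
| 6-week call | 5 | 1 | 0 |
| 3-month call | 2 | 0 | 0 |
| Total | 21 | 2 | 0 |

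**Step 3. The 3-month outcomes.** Suppose every scheduled item is done in all 50 women and nobody is lost. Compliance with the schedule is 21/21 = 100%, whether counted per item, per call, per procedure or per woman, and loss is 0%. VTE status and bleeding status at 3 months may still be blank in every woman, because neither is among the 21 items. This does not depend on how compliance is counted, only on study procedures meaning the items of the schedule.

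**Step 4. The scheduled bleeding forms.** Suppose both bleeding forms are missing in all 50 women and everything else is done. The rule requires more than 80%.

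| Reading of compliance | Result | Above 80%? |
|---|---|---|
| All scheduled items | 19/21 = 90.5% | Yes |
| Items from dosing day on | 14/16 = 87.5% | Yes |
| Items on the three calls | 10/12 = 83.3% | Yes |
| Calls or visits made | 100% | Yes |
| Items on the 3- and 6-week calls | 8/10 = 80.0% | No |
| Adherence, bleeding and quality-of-life forms | 4/6 = 66.7% | No |
| Each procedure separately (bleeding) | 0% | No |
| Women with every item done | 0/50 = 0% | No |

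**Step 5. The indirect limit.** Pooled over 50 × 21 = 1050 items, more than 80% means at least 841 done, so at most 209 missing (209/1050 = 19.9%). Total missingness of scheduled items is therefore bounded, but its place is not: the two bleeding forms account for 50 × 2 = 100 items and fit within 209.

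Loss can be added on top. If k women are lost just after the dosing day, each has 9 of 21 items, and the others have 19. The pooled share is (950 − 10k)/1050. It is 850/1050 = 80.95% at k = 10, which passes, and 840/1050 = 80.0% at k = 11, which does not.

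**The case against.** A reader might infer that the plan puts no limit at all on missing data, or that a pilot without a single bleeding form would pass. The document supports neither as a general statement. The compliance and loss criteria do bound missing scheduled items, at 19.9% on the pooled reading, and the bleeding form is itself a scheduled item that counts against compliance. The bleeding scenario passes or fails according to a denominator that the protocol does not give, and it fails on four of the eight readings above. It is also extreme: every woman would be reached at 3 and 6 weeks, with everything recorded on those calls except bleeding. Nothing suggests that this pattern is likely.

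The definition of compliance may stand in a statistical analysis plan that is not shown, and leaving it there would be ordinary practice. Not every feasibility outcome needs a threshold, and missing data will be reported with a confidence interval. The stated purpose of the pilot is enrollment, adherence and feasibility rather than ascertainment of outcomes by name. All of this stands, and it keeps the point narrow.

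It can also be said that the absent 3-month items are a fault of the schedule and not of the go rule, and that study procedures may reach beyond the schedule: the protocol requires a 12-week telephone contact, imaging of symptomatic women, and committee review of any VTE or bleeding event. This weakens the point only in part. A call can be made and counted without the outcome being asked. Imaging and committee review deal with events that have come to light; they do not separate a woman known to be event-free from one whose status was never recorded. And the list of four criteria is fixed in the protocol itself, so a later definition of compliance would not add a criterion for missing data.

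**Conclusion.** The point holds in this form: missing data is a declared primary outcome, the go rule contains no criterion tied to it, and the two nearest criteria limit it only indirectly. The firmest part is at 3 months. Full compliance with the schedule and no loss to follow-up are compatible with VTE and bleeding status unrecorded in all 50 women, so the pilot could proceed under the current protocol without having shown that these outcomes can be collected. This assumes that study procedures are those in the Trial Schematic Timeline.

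The bleeding-form result (90.5% over all items, 83.3% over the three calls) is secondary and conditional. It rests on pooling over scheduled items, and it reverses on stricter readings. It shows that the verdict on an absent safety outcome turns on an undefined denominator; it does not show that such a pilot would pass. Nor can one conclude that the pilot's outcome data will be largely blank. The pilot remains usable, but the change should be made before the go decision is taken.

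**What to change.** 1. Add VTE status and bleeding status to the 3-month call in the Trial Schematic Timeline. Without this, a completeness criterion at 3 months would have no scheduled item to rest on.
2. Keep the four existing criteria and add a fifth, applied to each outcome separately. For example: *VTE status and bleeding status at 3 months each recorded in > 80% of women not lost to follow-up.*
3. State the unit (item, form, call or woman) and the denominator of the compliance criterion.

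The fifth criterion must agree with the loss limit. A loss below 25% allows 12 of 50 women to be lost (24%), which leaves at most 38/50 = 76% known. A requirement of more than 80% known among all randomised women would allow only 9 unknown (41/50 = 82%) and would silently tighten the loss limit. The example avoids this by excluding women already counted as lost. With nobody lost it requires 41 of 50. With 12 lost it requires 31 of 38 (81.6%), which is 31/50 = 62% of all randomised women. If the sponsor prefers all randomised women as the denominator, the threshold should be set jointly with the loss limit. The 80% is borrowed from the existing criteria and is illustrative.

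The cost is two more questions on a call that is already planned, a few lines of text, and a go rule that is slightly harder to pass.

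### The protocol commits the pilot outcomes to a definitive trial under the current protocol, yet announces different ascertainment for that trial and a design informed by those same outcomes

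*Protocol*

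**What the plan says.** Under Sample size calculation the protocol plans 50 patients, 25 per strategy, and adds: "The outcomes from these patients will be included in the definitive trial". No condition is attached. Under Statistical analysis, the study "will proceed to a full trial under the current protocol if all the criteria below are met". The four criteria are recruitment, adherence to study drug, compliance with procedures, and loss to follow-up.

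Other sections describe how the definitive trial will differ:

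- Randomization: masking "will not be used in the pilot but a placebo control for ASA is intended for the definitive trial".
- Confirmation of VTE: "For the definitive trial, imaging will be adjudicated". In the same section: "Imaging will not be performed on all patients, only those with symptoms".
- Significance: the results will be used to design a large multicentre trial, and all the pilot's clinical outcomes will inform its final design.
- Data Safety Monitoring Committee: one hematologist and one obstetrician will review any VTE or bleeding event.

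For the analysis, the pilot is descriptive: "the clinical endpoints will only be presented using descriptive statistics". For the definitive trial, VTE, bleeding and "event-free outcomes will be compared between the two arms using a stratified log-rank test". On the margin: "A non-inferiority margin of 1.0 % will be used based on expert opinion".

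**The concern.** Pilot patients can be carried into a main trial when treatments, masking and endpoint ascertainment stay the same and the inclusion rule is fixed in advance. Here the inclusion rule is fixed, but the protocol itself announces that the other conditions will change. Followed as written, outcomes collected open label, with no blinded adjudication stated, and already examined to shape the design, would become part of a non-inferiority trial with different ascertainment.

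Two kinds of outcome are exposed in different ways. VTE needs imaging confirmation, which protects it in part, but only symptomatic women are imaged, and in the pilot they know their treatment. Bleeding is collected by telephone questionnaire from women who also know their treatment.

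The source of the data for a confirmatory comparison should be settled before results by arm are seen. If the contradiction is left in place, someone will have to decide later which sentence prevails, possibly with the pilot results in hand.

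**Working it through.** **The text, side by side.**

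1. Current protocol against definitive trial. The current protocol has no placebo, reserves adjudication of imaging for the definitive trial, and covers one centre. The definitive trial will have adjudicated imaging (firm) and several centres (firm), and a placebo for ASA is intended. A trial with adjudication and several centres is not run under the current protocol.
2. Inclusion against changed ascertainment. The inclusion sentence has no exception for a change in masking or adjudication. The four go criteria are feasibility criteria, and none tests whether the design stayed the same.
3. Inclusion against use for design. The pilot's clinical outcomes are to inform the definitive design and also to be counted in the trial so designed.
4. Possible rescue by the safety committee. Its review of every VTE and bleeding event is not said to be blind to arm or to be endpoint adjudication. It therefore does not supply what the definitive trial will have.

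**Scale.** The protocol's own figure is 25 + 25 = 50, which agrees. It gives no alpha, power or sample size for the definitive trial, so these are assumed below.

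Inputs from the protocol: margin 1.0% (Statistical analysis), read as an absolute risk difference; VTE with postpartum prophylaxis 1.7%, 95% CI 1.2% to 2.7% (Background), taken as the three-month rate in both arms. The risk difference stands in for the planned stratified log-rank test.

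n per arm = 2p(1 − p)(z_alpha + z_beta)² / 0.01²

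Example, p = 0.017, one-sided 2.5%, 80% power: 2 × 0.017 × 0.983 × (1.960 + 0.842)² / 0.0001, which rounds up to 2,624 per arm, or 5,248 in all. Pilot share: 50 / 5,248 = 0.95%.

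| VTE rate | One-sided alpha | Total n, 80% / 90% power | Pilot share |
|---|---|---|---|
| 1.2% | 2.5% | 3,724 / 4,984 | 1.34% / 1.00% |
| 1.7% | 2.5% | 5,248 / 7,024 | 0.95% / 0.71% |
| 2.7% | 2.5% | 8,248 / 11,042 | 0.61% / 0.45% |
| 1.2% | 5% | 2,934 / 4,062 | 1.70% / 1.23% |
| 1.7% | 5% | 4,134 / 5,726 | 1.21% / 0.87% |
| 2.7% | 5% | 6,498 / 9,000 | 0.77% / 0.56% |

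Expected VTEs in the pilot: 50 × 0.017 = 0.85 (0.60 at 1.2%, 1.35 at 2.7%).

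**Type I error and power.** Exact binomial enumeration, Wald test, one-sided 2.5%. Pooled means n per arm; excluded without replacement means n − 25 per arm.

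- Type I error (true difference 1.0 point) at 1.7% and 80% power: 0.0267 pooled, 0.0270 excluded. At 90% power: 0.0265 and 0.0265. Over 1.2% to 2.7% the two differ by at most 0.0004, in either direction. The excess over 0.025 comes from the Wald test, not from pooling.
- Power at equal rates, 1.7%: 0.8009 to 0.7962 (80% design) and 0.9002 to 0.8965 (90% design). Across 1.2% to 2.7% the change stays below 0.5 point.

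These type I figures assume the same ascertainment in both stages.

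**Bleeding, illustration only.** If open-label reporting distorted the pilot's between-arm bleeding difference by d points, the pooled difference would move by (25 / n) × d. With n = 2,624 and assumed d of 5, 10 or 20, that is 0.05, 0.10 or 0.19 points. Nothing in the protocol supports any particular d.

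**The case against.** The strongest reply is that almost nothing follows numerically. The pilot would be 1.7% of the definitive trial at most, about one VTE is expected in it, and the chance of none at a 1.7% rate is 0.983^50, about 42%. The pilot's own analysis and go criteria are untouched. The sentence says the outcomes will be included in the trial but names no analysis set. All of this stands and limits the size of the point. It does not remove the contradiction, because the protocol states the inclusion rule itself and does not leave it to a later document.

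The masking contrast is also weaker than it first looks. The placebo is only intended, and a placebo for ASA alone may not mask the arms, since control women inject for all 6 weeks (Intervention). Beyond masking, no change in how bleeding is ascertained is announced. The firm change is adjudication of imaging, which bears on VTE. This stands too, and the point rests first on adjudication.

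Use of the pilot for design is a modest obstacle: the non-inferiority aim, the margin and the test are already stated, and the margin comes from expert opinion.

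A reader might infer more than the text supports:

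- *That pooling inflates type I error.* The exact figures show it does not, given equal ascertainment.
- *That the trial continues on favourable efficacy results.* All four criteria concern feasibility.
- *That a single-centre pilot cannot be pooled.* Its centre could be one site of the later trial.
- *That pilot events can never be adjudicated.* The protocol neither provides for this nor excludes it.

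**Conclusion.** The point holds as a contradiction in the current text with a small numerical effect. Unconditional inclusion of the pilot outcomes and continuation under the current protocol do not fit with adjudicated imaging, an intended ASA placebo and a design informed by those outcomes. Neither the go criteria nor the safety committee's review resolves this.

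The conclusion about the text needs no assumption. The sizes in the table rest on assumed alpha and power, an absolute 1.0% margin, equal true VTE rates of 1.2% to 2.7%, and a risk difference in place of the log-rank test. The documents do not support a claim of material bias in the definitive result. The reasons to act are the integrity of the confirmatory data, agreement between sections, and a very low cost. It should be changed, but it does not threaten the pilot.

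**What to change.** Replace the inclusion sentence under Sample size calculation with: *Pilot patients will not be included in the primary analysis of the definitive trial; a sensitivity analysis may add them.*

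Alternatively, state before any by-arm review of pilot outcomes that they are included only if treatments, masking and endpoint ascertainment are unchanged and pilot events are adjudicated blind to arm by the definitive trial's process. Given the changes already announced, this condition may well not be met, so the first option is simpler.

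In either case, under Statistical analysis, say that the study proceeds to a full trial *under a definitive protocol*, so that the sentence agrees with Randomization, Confirmation of VTE and Significance.

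The change is to wording only. Up to 50 patients would not count toward the definitive trial. If they are not replaced, the loss is about half a point of power or less under the assumptions above (80.1% to 79.6% at 1.7% VTE).
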